## 11.2 Minor Protocol Deviations

The categories for the minor deviations may include, but are not limited to the deviations presented in Table 14. The assessment windows specified in the clinical study protocol are shown in Table 14.

**Table 14: Definition of Minor Protocol Deviation Categories**

Category	Description
Procedural violation	Violation of any study procedures not affecting safety or data evaluability.
Concomitant Medication	Use of any concomitant medications interfering with the “Smokers’ health profile” endpoints at Baseline, V7, V10, and V16. (See Appendix 2 of the study protocol)
Visit window deviation	See details in Table 15 for ambulatory visit window deviations. Visit window deviations for 24-hour urine are classified as major deviations.
Time missing	Assessment date or time is missing
Assessment missing	Assessment is missing
Visit missing	Scheduled visit not done

**Table 15: Assessment Windows**

Assessment	Nominal Time point(s)	Window
24-hour urine collection	V3, V7, V10, and V16	Start collection in the morning of the day prior to the visit, end after 24 ± 1 hours since the starting time
Ambulatory Visit	From V1 to V2	Not more than 42 days
	From V2 to V3	Not more than 5 days
	From V3 to V4	8 days ± 2 days
	From V4 to V5, and subsequent monthly visits	± 5 days with respect to the planned visit date.

## 12 PLANNED STATISTICAL METHODS

### 12.1 General Considerations

Data analysis will be performed using SAS® Version 9.2 or higher.

For analysis purposes, data collected in this extension study will be pooled with relevant data from the original study (ZRHR-ERS-09-US) as indicated in the following sections, with reference to Baseline and data collected during visits V1 to V10.

Data listings will be provided for all data collected as defined in the protocol, ordered by randomization arm, subject, Day, and study visit, unless otherwise stated. Summary statistics and statistical analysis will only be presented for data where detailed in this SAP. All unscheduled assessments will be included in the listings.

Markedly non-lognormally distributed BoExp and risk marker data will be transformed or analyzed by appropriate non-parametric methods with bootstrapping using the SAS procedure PROC SURVEYSELECT. The seed to be used in any analysis will be contained in the SAS output and will be different for each analysis.

This study has no formal pre-specified hypotheses associated with the study objectives. However, exploratory statistical hypothesis testing will be conducted to assess baseline comparability (see Section 12.3 “Demographics and Other Baseline Characteristics”) and to evaluate the THS 2.2 effect on selected endpoints (Section 12.7 “Planned Statistical Analyses”). All the THS 2.2 effect estimates will be accompanied by 95% CI.

### **12.1.1 Stratified Presentation**

Selected data will be presented as summaries stratified by sex (male and female) and average daily CC consumption level at V1 (“10-19 cig/day” vs. “>19 cig/day”), as described in this section.

Stratified presentations will be conducted by product use pattern categories within randomization arm for the FAS-EX at J]V4, V16[ for descriptive summaries of the following:

- Demographics (see 12.3 “Demographics and Other Baseline Characteristics”) by sex.
- Product use (see 12.7.2.1 “Product Use”) by sex and average daily CC consumption level at V1.
- “Smokers’ health profile” endpoints (see 12.7.1.3.6 “Descriptive Analysis of Primary Endpoints”) by sex and average daily CC consumption level at V1.

### **12.1.2 Subgroup Analyses**

Subgroup analyses will be based on the final covariates that are included in the primary analysis model. Potential covariates for subgroup analyses are presented in Table 3.

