12.5.4 Confirmatory Analysis

No formal confirmatory analysis is foreseen in this study.

FEV₁, HDL-C, and WBC will be analyzed in the real scale. Other clinical risk endpoints, which will be analyzed in the logarithmic scale, will be back-transformed to provide relative effects.

The primary analysis for the “smokers’ health profile” endpoints will be based on a mixed model for repeated measurements (MMRM). The model will include the endpoint value as the dependent variable, product use pattern category, visit (V7, V10, and V16), and exposure by visit interaction as fixed effects, with adjustment for site, sex, and Baseline endpoint value. In order to adjust for potential residual confounding, covariates found to be not balanced between THS-use and CC-use will be included in the final model. Modeling assumptions will be evaluated and model fit assessed by the analysis of residuals (model diagnostics) and by comparing the values predicted versus the observed endpoint values (calibration).

The point and interval estimate of the contrast of THS-use versus CC-use at V16 will be tabulated for the FAS-EX.

Supportive analysis will be conducted on the FAS-AR and PP set.

The detailed analysis methods, including subgroup analyses, are given in the SAP.

Confidentiality Statement

Data and information contained in this document are considered to constitute trade secrets and confidential commercial information, and the legal protections provided to such trade secrets and confidential information are hereby claimed under the provisions of applicable law. No part of this document may be publicly disclosed without the written consent of Philip Morris Products S.A.

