#### 4.1.4 Covariates for Smokers' Health Profile Analysis

The variables listed as “defined covariates” in Table 3 will be included in the analysis model. The “evaluated covariates” specified in Table 3 will be considered for their inclusion in the analysis model, as described in Section 12.7.1.2 Smokers' Health Profile Endpoints Evaluation”.

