### **12.1.7 Multiple Comparisons / Multiplicity**

This study has no formal pre-specified hypotheses associated with the study objectives. P-values and confidence intervals for all analyses are presented with no adjustment for multiplicity.

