### 12.7.1.2 Smokers' Health Profile Endpoints Evaluation

The following endpoints of the “smokers’ health profile” values at Baseline, at V7, at V10, and at V16 will be log-transformed (basee) prior to the analysis: sICAM-1, 11-DTX-B2, 8-epi-PGF2 $\alpha$ , COHb, and Total NNAL. HDL-C, WBC, and FEV1 will be analyzed in the original scale. Concentration of urinary clinical risk endpoints and BoExp will be adjusted for creatinine, as defined in Section 7.1.1 “Clinical Risk Endpoints and Biomarkers of Exposure in Urine”.

Clinical risk endpoints will be analyzed in the FAS-EX population for the subgroup comparing THS-use with CC-use categories, using a MMRM adjusting for sex, Caucasian origin, visit, value of the endpoint at Baseline and its interaction with visit, product use pattern category and its interaction with visit, and other Baseline covariates relevant for each specific clinical risk endpoint. Site will be included as a random effect [20]. Additional Baseline characteristics are defined for each endpoint of the “smokers’ health profile” in Section 4.1.4 “Covariates for Smokers’ Health Profile Analysis” and summarized in Table 3. Model will include terms for the “Defined Covariates” and for the subset of “Evaluated Covariates” selected if found to be significant at 10% level (between THS-use and CC-use) at Baseline for at least one of the 6-month (same as original study) or the 12-month product use categories (Table 15.2.3.1).

Modeling assumptions are evaluated and model fit is assessed by the analysis of residuals (model diagnostics) and by comparing the values predicted versus the observed endpoint values (calibration).

The SAS code for the mixed model to be used is shown below:

```
Proc mixed data=_data_ method=reml maxiter=200;  
Class subject product_use site sex caucasian_origin visit;  
Model endpoint = baseline sex caucasian_origin product_use visit  
                  product_use*visit baseline*visit <covariates> / ddfm=kr;  
Random site;  
Repeated visit / subject=subject type=un r rcorr;  
Lsmeans product_use*visit / slice=visit alpha=0.05 diff cl pdiff;  
Run;
```

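### SAP 12.1.2 takes its subgroup factors from each endpoint's final primary model, so they are partly chosen by a baseline-imbalance test and differ by endpoint; a fixed common list judged by interaction should replace it

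*SAP*

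**What the plan says.** Protocol 12.5.4 passes the matter on: "The detailed analysis methods, including subgroup analyses, are given in the SAP". SAP 12.1.2 answers in two sentences: "Subgroup analyses will be based on the final covariates that are included in the primary analysis model", and "Potential covariates for subgroup analyses are presented in Table 3".

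Table 3 (SAP 4.1.4) gives each endpoint two classes of covariate. For the first, "The variables listed as “defined covariates” in Table 3 will be included in the analysis model". The second class, the Evaluated Covariates, enters only if "selected if found to be significant at 10% level (between THS-use and CC-use) at Baseline", on either the 6-month or the 12-month use categories (SAP 12.7.1.2). The same section puts sex and Caucasian origin in every primary model; neither is in Table 3.

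SAP 12.1.1 separately fixes two factors for descriptive output: "Selected data will be presented as summaries stratified by sex (male and female) and average daily CC consumption level at V1". On multiplicity, SAP 12.1.7 states: "P-values and confidence intervals for all analyses are presented with no adjustment for multiplicity". SAP 12.1 limits presented statistical analyses to those the SAP details, and 13.4 and 16.4 describe the list of tables, figures and listings as complete.

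**The concern.** The rule uses a confounding criterion to choose effect modifiers. THS-use and CC-use are self-selected groups formed after randomization. A baseline difference between them shows who took up the product, which is a reason to adjust for a covariate. It gives no information on whether the THS effect changes across that covariate. A real effect modifier that happens to be balanced is left out, and an unbalanced covariate with no bearing on the effect is brought in.

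Two consequences follow. The list cannot be written down until the 12-month diary categories exist. And each endpoint may get a different list, so a subgroup finding for one component of the smokers' health profile may have no counterpart in another. BMI, for example, can become a subgroup factor for HDL-C but not for WBC.

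**Working it through.** The documents state no number of subgroups, so there is no stated figure to reproduce. The check counts Table 3, then compares sections.

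**1. Factors per endpoint (SAP Table 3)**

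| Endpoint | Defined | Evaluated | Possible factors |
|---|---|---|---|
| HDL-C | 2 | 5 | 2-7 |
| WBC | 2 | 3 | 2-5 |
| sICAM-1 | 2 | 1 | 2-3 |
| 11-DTX-B2 | 2 | 1 | 2-3 |
| 8-epi-PGF2α | 2 | 3 | 2-5 |
| COHb | 2 | 1 | 2-3 |
| FEV1 %pred | 1 | 8 | 1-9 |
| Total NNAL | 2 | 1 | 2-3 |
| All | 15 | 23 | 15-38 |

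Smoking intensity is the only factor guaranteed for all eight endpoints. Age is Defined for seven and only Evaluated for FEV1.

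**2. How much of the list chance could add.** If no covariate truly differed between the use groups, one test at 10% would admit 23 × 0.10 = 2.3 pairs on average. Two chances (6-month or 12-month categories) would admit at most about 23 × (1 − 0.9²) = 23 × 0.19 = 4.4 if the tests were independent. They are not, because the 6-month categories feed the 12-month ones. Self-selected groups may differ in truth, and then more would enter.

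**3. Cut-points.** The SAP defines levels for smoking intensity (two bands, Table 2), BMI (four classes, Table 2, although Table 3 treats it as continuous), Race/Ethnicity (five, Table 2) and other exposure (yes/no, Table 12). These cover 8 + 3 + 2 + 3 = 16 of the 38 pairs. The other 22 have no levels for subgrouping: age 8, smoking duration 5, diet 2, exercise 2, weight 2, alcohol 1, height 1, sleep deficit 1.

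**4. Sex and Caucasian origin.** By the first sentence of 12.1.2 both are subgroup factors, since both are in every primary model. By the second they are not, since Table 3 omits them. Counting them adds 8 × 2 = 16 pairs, giving 31 at the minimum. The maximum is 38 + 16 − 2 = 52, because Race/Ethnicity replaces Caucasian origin for WBC and FEV1 when selected.

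**5. Method and output.** SAP 12.1.2 names no model, population, visit or interaction test. Where the SAP wants an interaction judged, it says so: 12.7.3.2 sets 15.7% for propensity score by arm. The Section 16.4 tables by sex and by consumption level are descriptive; none is an inferential subgroup table.

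**6. Precision (side check).** Inputs from SAP Section 8: SD 6.4 %pred, 475 per arm, 65% enrolled, 60% THS-use, 20% lost or without usable diary data. Assumptions: all evaluable CC-arm subjects are CC-use, and the 20% either multiplies the 65% or is already contained in it.
- Multiplied: 475 × 0.65 × 0.8 = 247 CC-use and 0.6 × 247 = 148 THS-use. Half-width 1.96 × 6.4 × √(1/148 + 1/247) = ±1.30, within the stated ±1.5.
- Contained: 309 and 185, half-width ±1.17.
- A half-size subgroup multiplies this by √2: ±1.65 to ±1.84.
- The difference between two halves multiplies it by 2: ±2.33 to ±2.61.

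**The case against.** The other side has good points. The study tests no formal hypothesis, and its testing is called exploratory. Covariate selection follows a pre-specified rule on baseline data, and under SAP 6.3.2 the study statisticians stay blinded to the V16 primary values until SAP finalization or database lock, whichever is later. Endpoint-specific covariate lists are sensible for adjustment. A factor common to all eight endpoints exists, and it has a cut-point. All of this stands, and it limits the point to a poorly chosen rule for an exploratory analysis.

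A reader might go further and infer that the plan runs dozens of unadjusted subgroup tests, for example by doubling the 15 to 38 pairs to 30 to 76 contrasts and computing a family-wise error rate. The documents do not support that:
- The doubling assumes two levels for every factor. The SAP gives none for most pairs and more than two for others.
- No inferential subgroup table is listed.
- No family-wise level is claimed even for the eight primary endpoints.
- Within-subgroup contrasts are the wrong count. If THS has an overall effect, significant results within subgroups are true positives. A spurious subgroup effect is a false interaction.

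Nor do the documents show that sex is excluded, only that the two sentences of 12.1.2 disagree, or that selection is driven by outcomes.

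**Conclusion.** The point holds as a defect in the selection rule and its specification. The criterion in SAP 12.1.2 does not identify effect modifiers. It makes 23 of 38 possible Table 3 pairs conditional on a baseline test between self-selected groups, and it lets the list range from 1 to 9 factors for FEV1 against 2 to 3 for sICAM-1. Beyond that, 12.1.2 is ambiguous on sex and Caucasian origin, names no interaction test, leaves 22 of 38 pairs without levels, and has no matching output in Section 16.4.

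The counts come directly from Table 3 and need no assumption. The chance-selection figures assume no true baseline differences. The precision figures rest on the Section 8 planning inputs as combined above; the plan promises no precision for subgroups. They show only that a subgroup claim should not rest on a within-subgroup result. This is an inexpensive improvement to an exploratory analysis and does not affect the primary estimate.

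**What to change.** Replace SAP 12.1.2 with text to this effect:

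- Subgroup analyses of all eight endpoints use one fixed list, at least sex and average daily CC consumption at V1 (10-19 vs >19 cig/day), as in 12.1.1. Any further factor is named now, with its levels.
- The product_use-by-subgroup interaction contrast at V16 is reported with its 95% CI, beside the within-subgroup THS-use vs CC-use estimates and 95% CIs.
- All subgroup results are exploratory, and no subgroup effect is claimed from a within-subgroup p-value.

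Delete the link to the final model covariates and add the table to Section 16.4.

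The cost is SAP wording and one added interaction output per endpoint; both factors are already collected and coded. With two factors of two levels there are 8 × 2 = 16 interaction contrasts and 8 × 2 × 2 = 32 within-subgroup estimates. The gain is therefore a fixed, comparable list judged on the right quantity, not a smaller number of comparisons. The downside is that factors such as BMI are no longer subgroup factors unless named in advance. Subgroup estimates in FAS-EX still compare self-selected groups, which this change does not cure. The amendment belongs before database lock; after it, SAP Section 3 requires the change to be described in the study report.

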### **12.1.3 Descriptive Statistics**

In general, data are summarized by product use pattern category for FAS-EX and by randomization arm for the FAS-AR and PP populations for all visits during the 12-month randomized exposure period.

For the safety population, summaries will be in general produced by product use pattern category over the 12-month randomized exposure period, as described in Section 4.1.2.

For continuous data, summary statistics will include the number of subjects (n), the number and percent of subjects with missing data, the arithmetic mean, arithmetic standard deviation (SD), 95% confidence interval (CI) of the arithmetic mean, median, first and third quartiles, minimum, maximum; for log-normal data the geometric mean, geometric CV, and 95% CI of the geometric mean will be presented instead of arithmetic mean, SD, and 95% CI of the arithmetic mean. Post randomization summaries will include change from baseline apart from log-normal variables which will present % change and % relative change from baseline. For categorical data, frequency counts and percentages will be presented. For the calculation of summary statistics and statistical analysis, unrounded data will be used. Data listings will include all subject level data collected unless otherwise specified.

The following product labels will be used throughout the TFLs (Table 16):

**Table 16: Product Labels**

Product	Format used in TFLs	Order in TFLs
Tobacco Heating System 2.2	THS 2.2	1
Conventional cigarettes	CC	2

### 12.1.4 Handling of Dropouts or Missing Data (including outside the limits of quantification)

For the values of biomarkers and risk markers:

- Missing data at Baseline will be considered as missing completely at random, and only subjects with complete data for all the terms in the mixed model for repeated measures (MMRM) will be included in the analysis. Summary tables will include all available values.
- Missing data at Baseline for the propensity score analysis will be handled as described in Section 12.7.3.2 “Exposure/Response and Effect of Dual-Use on Smokers’ Health Profile”.
- Missing data after randomization will be considered as missing at random, and handled by means of MMRM approach.
- If more than 10% of the FAS-EX analysis population have missing data at Baseline or V16 for at least one of the primary endpoints, a sensitivity analysis will be conducted by means of a multiple missing imputation approach.

For laboratory parameters:

- Values below the lower limit of quantification (LLOQ) will be imputed using LLOQ/2. For values above the upper limit of quantification (ULOQ), the ULOQ will be used for calculation and reporting in summary tables.
- The number of values below LLOQ or above ULOQ will be presented in each summary table. If 50% or more data are below LLOQ or above ULOQ, only the number (%) of value below LLOQ or above ULOQ will be reported in the summaries, together with minimum (if no value below LLOQ is present) and maximum (if no value above ULOQ are present) of the observed values.
- For calculation of parameters derived as a ratio of two components (creatinine-adjusted 24-hour urine endpoints, Apo B/Apo A1) if the denominator is below LLOQ then the ratio will not be calculated and will be tabulated as “Not Calculated” in descriptive summaries and excluded from the main analysis. A sensitivity analysis

will be produced by including derived values using half LLOQ values for the denominator of the impacted endpoint for the FAS-EX.

- Missing data at Baseline will not be imputed.

For daily product use data:

- Missing product use data will be handled as specified in Section 16.3 "Data Handling and Derivation of Product Use Pattern Categories" and Section 12.7.1.3.3 "FAS-EX Supportive Analysis".

For calculation of questionnaires' scores:

- For MCEQ, domain or subscale scores will be derived by averaging the individual non-missing item scores if at least 50% are non-missing, otherwise they will be set to missing.
- For FTND questionnaire, the total score will be derived by summing the individual item scores if all items are non-missing; if any items are missing the total score will be set to missing.
- For SES questionnaire, observations with missing income or education will be excluded from the analysis of the composite SES.
- For assessment of cough, if no cough was reported at a given visit then the VAS score is imputed with zero for the calculation of change from baseline.

For Partial Dates:

- Partial dates will not be imputed for AEs, for medical history, and for concomitant medications, but assumptions will be made as follows to assign them to specific analysis categories:

Date information	AE Category	Disease Category	Medication Category
Missing or Partial date (e.g., --May2012, or ----2011). If month/year is the same as, or later than the month and/or year of Screening.	Product-emergent	Concomitant disease	Concomitant medication
Partial date, (e.g., --May2012, or ----2011). If month and/or year is earlier than the month and/or year of Screening.	Not product-emergent	Medical history	Prior medication

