## 12.4 Medical History and Concomitant Diseases

Medical history is defined as any condition that started and ended prior to V1. A concomitant disease is defined as any condition that is either detected at V1, and/or is still ongoing at V1.

Medical history and concomitant disease will be coded using Medical Dictionary for Regulatory Activities (MedDRA) version 18 or above and listed separately by randomization arm, System Organ Class (SOC) and Preferred Term (PT) within SOC.

Number and percent of subjects with Medical History and Concomitant diseases will be summarized by product use pattern categories (calculated over the entire 12-month ambulatory period), SOC and PT for the Safety population (Listing 15.3.1.9; Tables 15.2.1.5 and 15.2.1.6).

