### **12.7.4.2 Adverse Events**

A product emergent AE is defined as an AE that occurs at Enrollment or later. AEs that occurred at Enrollment will be considered product emergent only if flagged as having started after first THS 2.2 use in the eCRF. All other AEs will not be summarized but provided in listings only. Additionally, product emergent AEs flagged as having occurred after THS 2.2 use or with a start date greater than any recorded THS 2.2 use date will be summarized during the Product Trial period.

Any new, clinically relevant, abnormal finding or worsening of a pre-existing condition/concomitant disease detected during the study including the safety follow-up period will be documented as an AE and/or SAE as described in the Safety Management Plan.

All AEs occurring from the signing of informed consent will be recorded electronically. AEs collected before product use will be provided in listings only.

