#### **12.7.4.4 Vital Signs, Physical Findings and Other Observations**

##### **Related to Safety**

##### **12.7.4.4.1 Prior and Concomitant Medication**

Prior medication is defined as any medication that started and ended prior to Screening. Concomitant medication is defined as any medication starting on or after Screening. Medications that started prior to Screening and are ongoing at Screening are considered as concomitant.

All medications will be listed (Listing 15.3.6.4) by product using medicinal product and Anatomical Therapeutic and Chemical (ATC) codes (World Health Organization-Drug Dictionary Enhanced [WHO-DDE] Q1 2012 or later). A flag will be presented on the listing indicating whether the medication is prior or concomitant.

Prior and concomitant medications will be listed by randomization arm and will display original dates (no imputation). Concomitant medications will be summarized by randomization arm and separately by product use pattern category for the Safety population showing the number (%) of subjects who used the medication at least once by randomization arm and by ATC 1st and 2nd levels and medicinal product (Tables 15.2.6.24.\*).

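### Partially dated AEs are sorted against the Screening month although product-emergent is defined from Enrollment, so some events known to precede enrollment are counted as product-emergent

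*SAP*

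**What the plan says.** The partial-date rule in SAP 12.1.4 opens with "Partial dates will not be imputed for AEs, for medical history, and for concomitant medications" and then sorts incomplete dates with one two-row table. Row 1 covers wholly missing dates and partial dates that meet "If month/year is the same as, or later than the month and/or year of Screening". They become product-emergent AEs, concomitant diseases and concomitant medications. Row 2 covers partial dates that meet "If month and/or year is earlier than the month and/or year of Screening". They become not product-emergent, medical history and prior medication. Screening is the only reference point, and the table does not say whether the date is a start or a stop date.

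The definitions that the table serves are elsewhere in the SAP:

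- **AEs (12.7.4.2):** "A product emergent AE is defined as an AE that occurs at Enrollment or later". At the Enrollment visit itself the test is stricter: "AEs that occurred at Enrollment will be considered product emergent only if flagged as having started after first THS 2.2 use in the eCRF". AEs collected before product use are to be listed only. SAP 12.7.4.1 likewise restricts Screening-period safety data to listings unless otherwise specified.
- **Diseases (12.4):** "A concomitant disease is defined as any condition that is either detected at V1, and/or is still ongoing at V1". Medical history requires that the condition both began and ended before V1.
- **Medications (12.7.4.4.1):** "Medications that started prior to Screening and are ongoing at Screening are considered as concomitant". A prior medication must have both begun and ended before Screening.

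SAP Table 2 labels V1 as Screening and V3 as Enrollment. Table 15 limits V1 to V2 to "Not more than 42 days" and V2 to V3 to 5 days.

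**The concern.** For AEs, the table and the definition use different visits. Enrollment is the earliest point at which an event can be product-emergent, but the partial-date rule asks only whether the event could have begun in the Screening month or later. Some records therefore carry enough information to rule out emergence and are still called emergent.

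Protocol 12.6.4 makes AE data the primary assessment of safety, and AEs are recorded from informed consent, so records of this kind can exist. Events that precede both enrollment and randomization (V4) say nothing about either product. Counting them adds background events to the product-emergent tables and dilutes any real difference between arms.

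A second, weaker problem is in the same table. One date column drives all three classifications, with no statement of which date is meant and no check for ongoing status. Two programmers could implement the disease and medication columns differently.

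**Working it through.** **1. Does the rule agree with the definition?** Take V1 on 10 May 2015 and V3 on 20 June 2015, a 41-day gap, which is inside the 47-day limit.

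| Known AE onset | Result under 12.1.4 | What is known relative to V3 | Agreement with 12.7.4.2 |
|---|---|---|---|
| April 2015 | Not emergent | Before V3 | Yes |
| May 2015 | Emergent | Certainly before V3 | **No** |
| June 2015 | Emergent | Undetermined | Acceptable default |
| 2015 only | Emergent | Undetermined | Acceptable default |
| Missing | Emergent | Undetermined | Acceptable default |

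A year-only date can also go wrong when V1 and V3 straddle the new year. With V1 on 10 December 2014 and V3 on 20 January 2015, an onset of 2014 is certainly before V3 but is called emergent.

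**2. How much of the V1 to V3 window is affected?** The plan states no figure to reproduce. The inputs are the maximum gap from Table 15 (42 + 5 = 47 days), assumed shorter gaps because actual gaps are not reported, and onsets assumed evenly spread from V1 to the day before V3, averaged over all V1 dates in a 365-day year. An onset counts as known to be early if its calendar month precedes the V3 month.

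For a gap g of at most 28 days, a V1 date lying d days before the first of a month (d = 1 to g) gives d such onset days. With 12 month starts, the share is 12 × [g(g + 1)/2] / (365 × g) = 6(g + 1)/365.

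- g = 14: 6 × 15/365 = 90/365 = 24.7%
- g = 28: 6 × 29/365 = 174/365 = 47.7%

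For g = 47, V3 always falls in a later month than V1. If V3 is day k of its month, k − 1 of the 47 onset days share its month. The mean of k − 1 over the year is (7 × 465 + 4 × 435 + 378)/365 = 5373/365 = 14.72, from seven 31-day months, four 30-day months and February. The share is (47 − 14.72)/47 = 68.7%.

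Day-by-day enumeration gives the same three figures. The denominator is AEs with the day missing and onset between V1 and V3, not all AEs.

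**3. Disease and medication columns.** Take a drug started in 2011 (month and day unknown) and ongoing at Screening.

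- Read on the start date: 2011 is before Screening, row 2 applies, and the drug becomes a prior medication. This contradicts SAP 12.7.4.4.1.
- Read on the stop date: there is none, row 1 applies, and the drug is concomitant. This agrees with 12.7.4.4.1.

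A condition that began in 2011 and is ongoing at V1 behaves the same way against SAP 12.4. The result depends on a choice that the table leaves open.

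**The case against.** **Calling uncertain events emergent is the usual cautious default.** This stands for wholly missing dates, for onsets in the V3 month or later, and for year-only dates that do not settle the matter. It does not cover dates whose known part already rules out emergence.

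**Other text points the right way.** SAP 12.7.4.1 and 12.7.4.2 send Screening-period and pre-product events to listings, so the plan probably does not intend to count them. That shows an internal contradiction but does not resolve it, because the table in 12.1.4 is the only rule written for partial dates.

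**The effect is small and hides nothing.** This largely stands. The record must lack the day, begin between V1 and V3, and fall in a month before the V3 month. The window is at most 47 days, against about 52 weeks of exposure. The events precede randomization, so they should be balanced between arms in expectation. No efficacy analysis is touched.

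**A stronger reading of the medication columns.** A reader might infer that long-standing drugs and diseases with a partial start date are labelled prior or history even when ongoing, and so drop out of the concomitant summaries. The documents do not establish this. The table never says that the date is the start date, a stop-date reading gives the correct label, and SAP 12.4 and 12.7.4.4.1 state outright that ongoing items are concomitant. Nor does the point bear on the primary endpoints: interfering medication has its own deviation category in SAP Table 14, and the primary model in 12.7.1.2 has no medication term.

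**Conclusion.** The AE part holds. As written, SAP 12.1.4 contradicts 12.7.4.2 and gives a demonstrably wrong classification for AEs whose known onset month is the Screening month or later but before the Enrollment month. Among day-missing AEs beginning between V1 and V3, the misclassified share is about 25%, 48% and 69% for gaps of 14, 28 and 47 days. These figures assume evenly spread onsets, and the gaps are assumed; only the 47-day maximum comes from the SAP. They should not be read as shares of all AEs. The number of day-missing AEs in that window is not given and is probably small. The consequence is limited to descriptive safety tables.

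For diseases and medications the supportable finding is an ambiguity: the table conflicts with the SAP's own definitions only if it is programmed on start dates.

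**What to change.** Replace the single table in SAP 12.1.4 with separate rules.

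- **AEs:** compare the known part of the onset date with the month and year of Enrollment (V3). Classify as not product-emergent if it is earlier, or if the AE stop date is before V3. Otherwise keep product-emergent as the conservative default, including for wholly missing dates.
- **Diseases and medications:** state that classification uses the stop date or ongoing status at V1. Assign medical history or prior medication only if the stop date, or its known part, is before Screening. Items that are ongoing, or have no stop date, are concomitant whatever their start date.

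The cost is one small table and the matching code, before database lock. No new data are needed. The V3 date is on file, Protocol 8.2.1 and 7.3.1 already collect stop dates for AEs and medications, and the definitions in SAP 12.4 already require knowing whether a condition had ended by V1. Reporting the number of partially dated AEs with possible onset between V1 and V3 would bound the effect at almost no cost.
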